Official Title of the Study: Transmitted Light Tissue Analysis (TiLTT) (TiLLT)

Document Date: January 15, 2015

NCT Number: NCT02749201

Transmitted Light Tissue Thickness Analysis (TiL/TT) (TiLLT)

The most common surgical procedure for weight loss is the sleeve gastrectomy. The laparoscopic sleeve gastrectomy (LSG) involves the linear stapling of the stomach using a stapling device [e.g. Echelon (Ethicon Somerset NJ)] fired multiple times along the length of the stomach thereby excising 80-90% of the stomach leaving the patient with a "sleeve" of stomach rather than the normal anatomical pouch. The gastric wall varies in thickness and thus there are a varied staple sizes available for this use. Staple sizes range from 2.0mm-5.0mm in height. In standard surgical practice the surgeon chooses the size of staple cartridge for each subsequent firing based on his experience and estimations about the thickness of the stomach tissue in any given region. The drawback of this technique is that it is highly inaccurate. If the surgeon's estimation is in error, the staple height chosen may be either too tall or too short leading to bleeding or leakage from between the staples or malformed/unformed staples leading to staple line failure. Any of these errors can lead to devastating complications such as hemorrhage, leak, sepsis and death. To date there is no objective way to measure the thickness of the tissue being stapled and thus staple choice relies entirely on surgeon estimation which is inherently inaccurate. We hypothesize that a light source placed in the stomach lumen will transmit light through the gastric wall. The amount of light transmitted, i.e. visible to an imaging device arrayed external to the stomach, will be directly proportionate to the thickness of the stomach. This study will take advantage of the fact that during routine procedures in the sleeve gastrectomy procedure a lighted tube is placed into the gastric lumen via the mouth. This device is called the Gastrisail and has 10 separate LED lights arrayed along its length. This allows for the measurement of transmitted light intensity through the gastric wall at 10 individual locations along the length of the stomach. In addition this study will take advantage of the fact that during standard practice in a sleeve gastrectomy a section of the stomach corresponding to the location of the lights is excised and sent for pathological evaluation. This will allow us to measure the actual thickness of the stomach at 10 points corresponding to the locations of the transmitted light intensity. For this measurement we will use a standardized and validated measurement tool/calipers. Now with two sets of numbers we plan to correlate the degree of transmitted light intensity with actual thickness measurements and thereby reach an algorithm which will allow the transmitted light intensity data alone to predict gastric wall thickness. This will provide the surgeon with an entirely non-invasive objective measure of gastric wall thickness and hopefully improve his/her choice of staple size during these surgical procedures thus improving safety.

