
The aim of this project is to create a noninvasive method of predicting the thickness of the gastric wall. This information can then be used to aid the surgeon in picking the correct size staple cartridge when stapling the stomach during sleeve gastrectomy surgeries.

Methods: We propose to use a standard gastric sizing bougie (plastic guide placed into the stomach at the time of stapling designed to help outline a standardized staple line) used in

common surgical practice (Gastrisail, Covidien). This bougie comes with 10 LED lights arrayed along its length. The wavelength and light intensity of these LED's is standardized. The bougie is routinely placed via the mouth, down the esophagus and into the distal stomach. the bougie will be retained in place throughout the stapling process as per standard technique. The use of the bougie is part of the standard procedure of sleeve gastrectomy and is used in 100% of all sleeve operations.

Using a standard high definition laparoscope, images of these lights within the gastric lumen will be captured. The images will then be uploaded and processed using a software package provided by ImageIQ, Inc. The software will measure the light intensity at each of the 10 LED positions on the bougie, thereby obtaining 10 individual intensity readings at 10 different sites along the length of the stomach.

There will be no measurements made on the in-vivo stomach but simply an image made of the stomach with the lighted bougie in-situ. The analysis of the light intensity from the image and data extraction will be done after the completion of the surgery using software provided by the ImageIQ corporation.

The stomach will be stapled as per standard surgical routine and the specimen side of the gastric body will be separated from the remnant stomach and removed from the abdominal cavity as per standard surgical practice. Prior to this specimen being sent to the pathology department, on the back table, a standardized, validated thickness measuring tool will be used to measure the thickness of the gastric specimen ex-vivo at the identical 10 points as light intensity imaged at the LED's.

A mathematical formula will then be created to correlate the data obtained by light transmittance through the gastric wall and the mechanical measurements of the gastric specimen we obtained using a scientific calipers. The formula will be derived as a directly proportional calculation with where $y=kx$ and k is a non-zero constant.

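### A fitted y=kx gives a positive k even when light and thickness are unrelated, and the supplied text has no error measure or light-free comparator to show whether the formula predicts

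*Combined protocol and SAP*

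**What the plan says.** The opening background hypothesises that transmitted light "will be directly proportionate to the thickness of the stomach". It continues: "with two sets of numbers we plan to correlate the degree of transmitted light intensity with actual thickness measurements and thereby reach an algorithm". The stated purpose is to "allow the transmitted light intensity data alone to predict gastric wall thickness".

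The Methods section describes the two data sources. The software reads the image, "thereby obtaining 10 individual intensity readings at 10 different sites along the length of the stomach". The calipers then "measure the thickness of the gastric specimen ex-vivo at the identical 10 points". The formula linking them will be "derived as a directly proportional calculation with where $y=kx$ and k is a non-zero constant". The text does not say which variable is x and which is y.

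The closing paragraph, on data collection, gives 20 measurements per patient (10 light, 10 thickness) and says the algorithm will be constructed once all patients are in. It points to a statistical methodology further on, but none follows in the supplied document. Nothing supplied gives a number of patients, a correlation threshold, a test, an error limit in mm, a comparator or a validation step.

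**The concern.** A line forced through the origin behaves differently from an ordinary regression line. When both variables are positive, k mostly reflects the ratio of their average levels. It does not show whether thickness changes as light changes. The study can therefore produce a k, and hence a formula, from data in which light carries no information.

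A correlation does not close the gap. It measures how well the best line with a free intercept would fit, whereas the formula named in the plan has no intercept. A moderate positive correlation can coexist with a y=kx that predicts worse than giving every site the average thickness.

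The formula is the study's product and is meant to inform the choice of staple size. An unhelpful formula could be presented as a working one, and the supplied text contains nothing that would reveal it.

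**Working it through.** **Inputs.** From the document: the form y=kx, 10 light and thickness pairs per patient, and two non-negative variables. Taken here: y is thickness and x is light, because thickness is what is to be predicted; k is estimated by least squares. The document gives no means, spreads, correlation or number of patients, so those below are assumptions. It also states no figure that could be reproduced.

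**Step 1: sign of k.** k = Σxy / Σx². With x and y non-negative, k > 0 unless every product is zero. A k taken as mean y over mean x is also positive, and swapping x and y changes nothing.

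**Step 2: error of y=kx.** Write cx and cy for the coefficients of variation (CVs) of light and thickness, r for their correlation and μ for mean thickness.

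- MSE of y=kx: μ²[(1 + cy²) − (1 + r·cx·cy)² / (1 + cx²)]
- MSE of the mean thickness: μ²·cy²

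At r = 0 the first becomes μ²[cy² + cx²/(1 + cx²)]. This exceeds μ²·cy² whenever light varies at all, so with unrelated data y=kx always loses to the mean. That result needs no assumed values.

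**Step 3: size, with cx = 0.40 and cy = 0.25** (1 + cx² = 1.16; 1 + cy² = 1.0625; cx·cy = 0.10).

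| r | MSE of y=kx, divided by μ² | RMSE relative to the mean |
|---|---|---|
| 0 | 1.0625 − 1/1.16 = 0.2004 | √0.2004 / 0.25 = 1.79 |
| 0.5 | 1.0625 − 1.05²/1.16 = 0.1121 | √0.1121 / 0.25 = 1.34 |
| 0.7 | 1.0625 − 1.07²/1.16 = 0.0755 | √0.0755 / 0.25 = 1.10 |

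At r = 0.7 a line with an intercept has a relative RMSE of √(1 − 0.49) = 0.71. Light is then informative although y=kx loses.

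**Step 4: break-even correlation.** Equating the two MSEs gives r* = (√(1 + cx²) − 1) / (cx·cy). For 0.40 and 0.25 this is (1.0770 − 1)/0.10 = 0.77. With cy held at 0.25:

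| Light CV | r* |
|---|---|
| 10% | 0.20 |
| 20% | 0.40 |
| 30% | 0.59 |
| 40% | 0.77 |
| 50% | 0.94 |

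With light CV 50% and thickness CV 15%, r* is 1.57, so y=kx cannot beat the mean at any correlation.

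**Step 5: simulation check.** Light and thickness were drawn independently (lognormal, no patient effects), with assumed mean thickness 3 mm, cy = 0.25, cx = 0.1, 0.3 or 0.5, 10 to 100 patients with 10 sites each, and 2,000 runs per setting. In every run k was positive, a test of k = 0 rejected, and y=kx had a larger RMSE than the mean in newly drawn patients. With 20 patients and cx = 0.3 the average RMSE was 1.15 mm against 0.75 mm. An ordinary test of zero correlation rejected in only 3.6% to 6.2% of runs.

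**Step 6: when the hypothesis is exactly true.** If thickness = k × light + independent error, then r = cx/cy. Because √(1 + cx²) − 1 < cx²/2, r* is always below half of cx/cy, so y=kx always beats the mean. With cx = 0.20 and cy = 0.25, r = 0.80, r* = 0.40 and the relative RMSE is 0.60. The 40%/25% pair cannot arise from this model, since cx/cy would be 1.6. It requires noise in the light reading or a non-zero intercept.

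**The case against.** The strongest reply is that the phrase about a non-zero constant only defines direct proportionality. A reader might infer that the plan makes non-zero k a success test that cannot fail. The document does not say so, and it plans neither a t-test of k nor a no-intercept R-squared. With unrelated data at the 40%/25% spreads that R-squared would be 1/(1.16 × 1.0625) = 0.81, which is a reason not to adopt it, not a fault in what is written.

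A reader might also infer that no result could lead the study to a negative conclusion. That goes too far. Both the background and the Methods speak of correlating the two data sets, and a correlation can come out null, as Step 5 shows. The methodology referred to in the closing paragraph might also have held a criterion, and the supplied text cannot settle this. What stands is narrower: no decision rule, error measure or comparator is given there.

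Third, the illustrative spreads are invented, and under exact proportionality y=kx performs well (Step 6). This is correct and limits the point. Exact proportionality, however, is the hypothesis under study, and a positive correlation does not establish it.

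**Conclusion.** The point holds in this limited form. That k is positive whatever the relation, and that y=kx loses to the mean thickness when the two are unrelated, is algebra. A non-zero k is therefore no evidence of prediction, and a positive correlation alone does not show that y=kx works.

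The size depends on assumed spreads. At CVs of 40% and 25% the relative RMSE is 1.79 at zero correlation and 1.34 at 0.5, with break-even at 0.77. At thickness CV 25% the break-even runs from 0.20 to 0.94 as light CV goes from 10% to 50%. These are population values for least-squares k with thickness as y.

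A reader might infer that if y=kx loses to the mean, light does not predict thickness. That does not follow: at correlation 0.7 in Step 3, y=kx loses while a line with an intercept reduces the error. Nor do the documents show that y=kx will perform badly. They leave the question unanswerable as written.

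**What to change.** Add the following to the analysis section.

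1. Judge association by the slope of thickness on light, free in sign and with an intercept, after centring both within patient and with standard errors clustered by patient. Do not use k, its p-value or a no-intercept R-squared for this purpose.
2. Report RMSE in mm, leaving out one patient at a time, for three predictors: y=kx, a line with an intercept, and a light-free constant (the mean thickness in the other patients).
3. Present y=kx as a predictive formula only if its RMSE is lower than the constant's. If it is not, but the line with an intercept beats the constant, report that proportionality failed and give the intercept line.
4. Conclude that prediction from light was not shown only if the intercept line also fails to beat the constant.

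Also state which variable is x and which is y. If the statistical methodology mentioned in the closing paragraph exists, check these rules against it.

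The cost is a few sentences and a little more analysis of the 10 pairs per patient already planned. No new data, patients or procedures are needed. The study would then be able to report a negative result.

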This predictive algorithm will allow non-invasive gastric wall thickness measurements in real-time based solely on imaged light transmittance using nothing more than a standard lighted bougie and standard laparoscope.

The study will be conducted in the operating room and will have two halves of data collection. Firstly there will be images taken intraoperatively of the lighted bougie while in proper position within the gastric lumen. Secondly there will be gastric wall thickness measurements taken of the explanted stomach specimen on a back table in the operating room prior to it being sent to the pathology department. This data collection will yield 20 measurements per patient (10 from each of these two sources). Thus each patient will be enrolled in the study only intraoperatively. Following collection of the data for all included patients (see below statistical methodology) the data from each of these sources will be analyzed and the predictive algorithm constructed.

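### The available text plans a correlation and a proportional formula, then claims thickness measurement, without naming a prediction error in mm or an acceptable error

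*Combined protocol and SAP*

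**What the plan says.** The combined protocol and SAP justifies the study by the poor accuracy of the surgeon's estimate of wall thickness. Of current practice the background says: "The drawback of this technique is that it is highly inaccurate".

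The analysis is described in three places:

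- **Background:** "we plan to correlate the degree of transmitted light intensity with actual thickness measurements", in order to "reach an algorithm which will allow the transmitted light intensity data alone to predict gastric wall thickness".
- **Methods:** "The formula will be derived as a directly proportional calculation", that is, y = kx, where "k is a non-zero constant".
- **Closing paragraphs, on the algorithm and data collection:** "This predictive algorithm will allow non-invasive gastric wall thickness measurements in real-time based solely on imaged light transmittance". Each patient contributes 10 light readings and 10 caliper readings.

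The closing paragraph also points to a further section: "Following collection of the data for all included patients (see below statistical methodology". The available text ends without it.

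The only figures in mm are in the background: "Staple sizes range from 2.0mm-5.0mm in height". They describe the staples on offer and are not an error limit.

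**The concern.** The formula is meant to return a thickness that helps the surgeon choose a cartridge. What matters for that use is how far the predicted thickness may lie from the caliper thickness, in mm. The available text names no quantity that measures this: no root mean squared error, mean absolute error or limits of agreement. It states no error that would be acceptable, and no prediction of patients who were not used to fit the formula.

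A correlation has no units. It says how closely two sets of readings rank and move together in this sample, and it depends on how much thickness varies among the sites measured. A fitted constant does not bound the error in mm either. As written, the study could report a good correlation and a value of k, and conclude that thickness can be measured from light, with a formula too inaccurate for its purpose.

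The stake is the conclusion drawn. Safety within the study is not in question: the images are analysed after surgery and no study patient is managed by the formula.

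**Working it through.** **Figures to reproduce.** The available text gives no sample size, power, SD, correlation or margin. Its only arithmetic is 10 + 10 = 20 measurements per patient, which is consistent.

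**Question.** If the study reports a given correlation r, what error in mm does that imply?

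**Inputs.**
- Thickness SD: assumed, 0.5, 0.75 and 1.0 mm. Not in the documents.
- Correlation r: assumed, 0.8, with 0.6 and 0.95 as alternatives. Not in the documents.
- Span of staple heights: 5.0 − 2.0 = 3.0 mm, from the background. Used only as a scale.

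**Formula.** For a calibrated linear predictor (a line with an intercept), the 95% error half-width is 1.96 × SD × √(1 − r²). This takes errors as roughly normal with constant spread. It ignores uncertainty in the fitted line and the clustering of ten points within a patient.

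**Same correlation, different SD.** At r = 0.8, √(1 − 0.64) = 0.6.

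| Assumed SD (mm) | Calculation | 95% half-width (mm) |
|---|---|---|
| 0.5 | 1.96 × 0.5 × 0.6 | 0.59 |
| 0.75 | 1.96 × 0.75 × 0.6 | 0.88 |
| 1.0 | 1.96 × 1.0 × 0.6 | 1.18 |

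**Same SD, different correlation.** At SD 0.75 mm:

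| Assumed r | Calculation | 95% half-width (mm) |
|---|---|---|
| 0.6 | 1.96 × 0.75 × 0.800 | 1.18 |
| 0.8 | 1.96 × 0.75 × 0.600 | 0.88 |
| 0.95 | 1.96 × 0.75 × 0.312 | 0.46 |

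**Reading.** One value of r corresponds to a twofold range of error (0.59 to 1.18 mm) across these SDs. The full width of the 95% range is 2 × 0.59 = 1.18 mm at the lower end and 2 × 1.176 = 2.35 mm at the upper end, or 39% and 78% of the 3.0 mm span. A reader given only r could not tell these cases apart.

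**Link to y = kx.** The best line with an intercept has the smallest root mean squared error of any straight line, including those through the origin. A proportional formula therefore cannot have a smaller one at the same SD and r. How much larger it would be depends on where the measurement noise lies, which the documents do not say.

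**The case against.** The strongest objection is that the absence is unproven. The text sends the reader to a statistical methodology section, where an error measure would naturally stand, and that section is not in the available file. This stands. A reader might infer that the full plan has no accuracy measure at all. The documents do not support that, so the first step is to check.

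A second objection is that the wording states a purpose and is not a decision rule. In the background the prediction claim sits inside a sentence about what the investigators plan, the Methods aim is to create a method, and the benefit for staple choice is only hoped for. This is right for the background. The statement in the closing paragraphs carries no such qualification.

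Two stronger readings are tempting and should be resisted:

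- **That a non-zero k is the test of success.** That phrase is part of the definition of direct proportionality. Nothing says that a non-zero k would count as a positive result, and the planned correlation would itself show if light and thickness were unrelated.
- **That y = kx must be biased or less accurate than a line with an intercept.** Under exact proportionality this follows only if the noise is placed in the light reading. If it lies in the caliper reading, the bias and the extra error vanish.

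A third objection is that the remedy should be no heavier than the gap. This also stands. A formal pass rule on the confidence bounds of both limits is debatable and is not part of this point. Nothing in these objections turns a correlation into an error in mm.

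**Conclusion.** The point holds for the available text and should be addressed, subject to the missing section. The stated analysis is a correlation and a proportional formula. The stated conclusion is that thickness can be measured from light. Nothing in the available text connects the two through an error in mm.

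The illustrative size is a 95% half-width of about 0.59 to 1.18 mm at r = 0.8, and of 0.46 to 1.18 mm at SD 0.75 mm as r falls from 0.95 to 0.6. These figures rest on assumed SDs and correlations and say nothing about what the study will find. The conclusion does not depend on them, because r alone never fixes the error in mm. Confidence is medium, because the cited section has not been seen.

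**What to change.** First confirm whether the statistical methodology section names an error measure and an acceptable error. If it does not:

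1. Make the primary result the prediction error in mm, predicted minus caliper, with mean error and 95% limits of agreement.
2. Predict each patient from a formula fitted without that patient.
3. Take confidence intervals over patients, not points, because ten points from one stomach are not ten independent observations.
4. Have the investigators state an acceptable error in mm before analysis.
5. Make the claim in the closing paragraphs conditional on the observed error. If the error exceeds the stated limit, report it without the claim.
6. Keep the correlation as a descriptive result.

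**Cost.** Some wording and a short analysis of data already planned, with no extra procedure. The headline may look less favourable than a correlation coefficient, and the investigators commit to an acceptable error in advance. The limits may be wide if patients are few. The available text shows no sample size, so it cannot be judged how precise they would be.

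### The pooled light-only y = kx fit has no within-position check, so a positive correlation could reflect site along the stomach instead of wall thickness

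*Combined protocol and SAP*

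**What the plan says.** The Methods section of the combined protocol and SAP describes image analysis at each LED on the bougie, "thereby obtaining 10 individual intensity readings at 10 different sites along the length of the stomach". Calipers are then applied to the specimen at the matching points, and the data collection paragraph gives the count: "This data collection will yield 20 measurements per patient (10 from each of these two sources").

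Methods specifies one model: "The formula will be derived as a directly proportional calculation with where" y = kx, with k a non-zero constant. It has no intercept, site term or patient term. Light is the only predictor. The background aims for "an algorithm which will allow the transmitted light intensity data alone to predict gastric wall thickness", and the paragraph after Methods describes real-time measurement "based solely on imaged light transmittance using nothing more than a standard lighted bougie and standard laparoscope".

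Three other statements bear on the point:

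- The background says "The gastric wall varies in thickness and thus there are a varied staple sizes available for this use", and that surgeons now choose staples from experience and "estimations about the thickness of the stomach tissue in any given region".
- Methods says that the wavelength and output of the LEDs are standardized.
- The closing paragraph says "Following collection of the data for all included patients (see below statistical methodology) the data from each of these sources will be analyzed". No such methodology section follows in the available text.

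**The concern.** The ten sites are ordered, and the background implies that thickness differs by region. One constant fitted to all pairs mixes two sources of association: differences between sites, and differences between stomachs at the same site. Only the second shows that light says something about the wall beyond where along the stomach one is looking.

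Suppose recorded light also changes along the bougie for reasons unrelated to thickness, in the same direction as the thickness gradient. The pooled correlation is then positive even if light and thickness are unrelated at every site. Light would add nothing to knowing the region, and the stated analysis contains no comparison that would show this. The intended use is choice of staple cartridge, so it matters whether light adds information beyond region.

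**Working it through.** **The plan's own figure.** 10 light + 10 caliper readings = 20 values, or 10 pairs, per patient. This agrees. The available text gives no number of patients, SD, gradient or power, so every input below is an assumption.

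**Model.** I read y as thickness and x as light. Position p takes 10 equal steps from 0 to 1, with variance V = 0.1019.

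- Thickness (mm) = 3 + g(p − 0.5) + patient effect (SD 0.3) + residual (SD 0.4). The variance within a position is 0.09 + 0.16 = 0.25.
- Light = 2 + d(p − 0.5) + b(thickness − 3) + noise (SD 0.3).
- A (drift only): b = 0. B (true tracking): d = 0.

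**Formulas.** k = E(xy)/E(x²). The error of kx is √[E(y²) − k·E(xy)].

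- Pooled r in A = gdV / √[(g²V + 0.25)(d²V + 0.09)].
- Within-position r is 0 in A, and 0.5b / √(0.25b² + 0.09) in B.

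**A, g = 2 mm, d = 0.5 (1.7 SD of light noise).**

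- E(xy) = 6 + 2 × 0.5 × 0.1019 = 6.102; E(x²) = 4 + 0.0255 + 0.09 = 4.1155; k = 1.48.
- E(y²) = 9 + 0.4074 + 0.25 = 9.657; error = √(9.657 − 6.102²/4.1155) = 0.78 mm.
- Pooled r = 0.1019 / √(0.6574 × 0.1155) = 0.37.

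**Comparison at g = 2 mm.** In the weak-tracking row, b = 0.147 is solved so that pooled r equals that of A.

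| Light | k | Pooled r | kx error (mm) | Within-position r |
|---|---|---|---|---|
| Noise only, no drift | 1.47 | 0.00 | 0.92 | 0.00 |
| A, aligned drift 1.7 SD | 1.48 | 0.37 | 0.78 | 0.00 |
| A, reversed drift 1.7 SD | 1.43 | −0.37 | 1.10 | 0.00 |
| B, weak tracking, b = 0.147 | 1.49 | 0.37 | 0.78 | 0.24 |
| B, strong tracking, b = 0.67 | 1.47 | 0.88 | 0.45 | 0.74 |

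Benchmarks at g = 2: predicting the overall mean gives √0.6574 = 0.81 mm; predicting the position mean gives √0.25 = 0.50 mm.

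**Larger drift (d = 1, 3.3 SD), g = 2.** Pooled r is 0.57 in A and in the matched B. The error is 0.69 and 0.67 mm, and within-position r is 0.00 and 0.40.

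**Smaller gradient, g = 1.** In A with d = 0.25, 0.5 and 1, pooled r is 0.14, 0.25 and 0.39. For d = 0.5 the error is √(9.352 − 6.051²/4.1155) = 0.67 mm; across the three it is 0.67 to 0.70 mm. The overall mean does better: √0.3519 = 0.59 mm.

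**What k shows.** Pure noise gives k = 6/4.09 = 1.47, close to mean thickness over mean light (3/2). A non-zero or stable k is therefore no evidence for or against tracking.

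**What separates A from weak B.** Adding light to position changes the error from 0.50 to 0.50 mm in A, and from 0.50 to 0.50 × √(1 − 0.24²) = 0.49 mm in B. Error alone barely distinguishes them; the within-position association does. With g = 2, drift 1.7 SD, 2,000 simulated trials each and a patient-clustered t test:

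- The pooled association is significant in 94–100% of trials in both A and B.
- The within-position association is significant in 5–7% in A, and in B in 58%, 89%, 97% and 100% with 10, 20, 30 and 50 patients.

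**Other assumed inputs** (within-patient SD 0.3 mm, light noise 0.1 on a scale with mean 1, stronger tracking, 50 patients). For gradients of 1 and 2 mm, pooled r is 0.44 and 0.76 for site-only light against 0.87 and 0.93 for true tracking. The kx error is 0.52 against 0.30 mm, and the site-mean error is 0.42 mm. Within-position r is about 0.00 against 0.81.

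**The case against.** The strongest reply is that the harm rests on a drift that the document does not describe. Standardized LEDs remove the most obvious cause. The drift must also run the same way as the thickness gradient, since reversed drift gives a negative correlation that would not look like support for direct proportion. This stands as a limit. It does not close the question, because standardizing the source does not standardize the image, and no control of distance, angle or exposure by site is stated.

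Second, A and B look alike largely because B was set to weak tracking. Strong tracking would show itself in a higher pooled r and a lower error, and at a 1 mm gradient drift-only light predicts worse than the overall mean. This also stands. The ambiguity concerns modest correlations, and the plan states neither a benchmark nor a threshold by which to judge one.

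Third, the missing methodology section may already deal with position. That cannot be excluded, and its absence from the available text is not counted as an error.

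A reader might infer three stronger claims that the document does not support:

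- That the study cannot separate thickness from site. The matched pairs allow it; only the stated analysis does not.
- That equal values of k demonstrate confounding. They follow from the no-intercept form, as the noise row shows.
- That treating the ten pairs as independent is a separate mistake. The available text promises no interval or test, so clustering only governs how any interval should be computed.

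**Conclusion.** The point holds in a limited form. In the available text, the one stated analysis cannot tell light that follows wall thickness from light that follows site, if drift unrelated to thickness exists and is aligned with the thickness gradient. With no drift the problem disappears.

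Its size is unknown. The simulated values are illustrations under assumed gradients of 1 to 2 mm and drifts of 0.8 to 3.3 SD; in that range drift alone produces pooled r of 0.14 to 0.57. The background does not show that surgeons already hold the regional information in any precise form. It calls their present estimates inaccurate, so a position-only model is a benchmark and not a description of current practice.

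Priority is low to moderate: the check is nearly free and bears on the plan's central claim, but nothing in the text shows that the problem will occur.

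**What to change.** Keep y = kx as the main formula and add the following before analysis:

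1. Store the patient and LED number with every pair.
2. As a pre-stated secondary analysis, report the light–thickness association within LED position with its interval. Patients are the unit: use a whole-patient bootstrap, or a patient-clustered standard error with a small-sample correction.
3. Report the leave-one-patient-out error of the formula in mm beside two benchmarks, the overall mean thickness and a position-only model.
4. Conclude that light adds information beyond region only if the within-position association supports it. State in advance that a small position-adjusted coefficient does not by itself show that light fails, because a regional gradient that light truly follows is real signal.
5. If the cited methodology section already covers this, refer to it instead.

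The cost is some analysis text and a few lines of code, with no new data. The within-position check has limited power with few patients (about 58% with 10 in the example), so it should be reported as an estimate with its interval and not as pass or fail.
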